### 13.2 Safety Laboratory Assessments

Blood and urine samples will be collected at the time points specified in the Schedule of Events (refer to the Protocol) to conduct hematology, serum chemistry, coagulation, urinalysis analyses & microscopic urinalysis, and thyroid function.

The following tests will be performed:

Hematology:

- Hemoglobin
- Hematocrit
- Red Blood Cell Count
- Mean Corpuscular Volume
- Mean Corpuscular Hemoglobin
- White Blood Cell Count
- Neutrophils
- Neutrophils (%)
- Lymphocytes
- Lymphocytes (%)
- Monocytes
- Monocytes (%)
- Eosinophils
- Eosinophils (%)
- Basophils
- Basophils (%)
- Platelets

Serum Chemistry:

- Sodium
- Potassium
- Chloride
- Bicarbonate
- Calcium
- Magnesium
- Phosphorus
- Blood Urea Nitrogen
- Creatinine
- Blood Glucose
- Alanine aminotransferase (ALT)
- Aspartate aminotransferase (AST)
- Alkaline Phosphatase (ALP)

- Total Bilirubin
- Total Protein
- Albumin
- Lactate dehydrogenase (LDH)
- Amylase
- Uric acid
- Lipase

#### Coagulation

- Prothrombin Time (PT)
- Activated Partial Thromboplastin Time (aPTT)
- Partial thromboplastin time (PTT)
- International Normalized Ratio (INR)

#### Urinalysis & Microscopic Urinalysis:

- Bilirubin
- Protein
- pH
- Blood
- Specific Gravity
- Ketones
- Glucose
- Microscopic Examinations

#### Thyroid Function:

- Triiodothyronine (T3)
- Free triiodothyronine (FT3)
- Free Thyroxine (FT4)
- Thyroid-Stimulating Hormone (TSH)

All laboratory data collected at scheduled and unscheduled visits will be included in the listings, but only results collected as scheduled visits will be included in the summary tables.

Results for individual parameters may be reported in different units depending on the analyzing laboratory. The results (and the corresponding normal range cut-off values) for individual parameters will be converted to International System of Units (S.I.) units to summarize the data.

For all the parameters where a unit value has been reported, the parameter names that will be used in the outputs will comprise of the test name and the unit of measure, for example, 'Albumin (g/L)'. For the urinalysis parameters, the parameter name will be the reported test name only. Parameters will be sorted alphabetically within tables and listings.

For all parameters where a normal range limit value was reported, the normal range will be derived based on the available lower and upper limit values and any reported mathematical symbols. If both a lower and upper limit value is available, the normal range will be presented as '(Lower, Upper)'.

The hematology, serum chemistry, coagulation, urinalysis analyses & microscopic urinalysis, and thyroid function results tables will present summary statistics for each laboratory parameter within the specific test panel. For each parameter, summaries will be presented for the baseline and each scheduled post-baseline visit. In addition, summaries will be presented for the change from baseline values at each scheduled post-baseline visit (continuous descriptive analysis).

The decimal precision to which the summaries for each parameter will be based on the maximum number of decimals to which the reported result or the normal range limits are presented to in the raw data. The results and normal ranges will be displayed to the same decimal precision in the listings.

A cross-tabulation of the worst grade that observed in planned and unplanned visits until ED/EOT versus the baseline grade will be presented with shift table for both of the NCI-CTCAE grade and investigator's clinical significance abnormality assessment.

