- t. Response Assessment: Initial response assessment will be performed after the first 2 cycles, then every 2 cycles for the first year, followed by every 3 cycles thereafter for up to 2 years (i.e., ± 7 days of C3D1, C5D1, etc.) and at any time per investigator's discretion and at ED/EOT (unless clear PD has been documented previously).
- u. All Early Discontinuation / End of Study Treatment (ED/EOT) assessments must be performed within 14 days following the subject's last administration of study treatment and prior to initiation of any other treatment, whichever comes first.
- v. All AEs must be recorded and followed through 30 days following cessation of study treatment (or 30 days after final dose if the subject initiates new anticancer therapy), or until resolution, whichever comes first.
- w. Serious adverse events will be collected after the consent form is signed through 90 days following cessation of study treatment, or 30 days after final dose if the subject initiates new anticancer therapy, whichever occurs first.
- x. 30 days from the final dose of study treatment.
- y. Data regarding post-study anti-tumor therapy and survival will be collected from all subjects who receive ≥ 1 dose of FLX475 or pembrolizumab. All subjects who discontinue study drug will be followed for survival and any post-study anticancer treatment via at least every 3 months (± 7 days). This long-term follow-up information will be gathered during routine clinic visits, other site contact with the subjects, or via telephone or e-mail with the subjects/caregivers or referring physician offices. These data will be collected in the source documents (e.g., subject medical record) and transcribed into a specific eCRF.
- z. All time points of the assessments are based on FLX475 administration.
- aa. Laboratory Screening Tests (Serum chemistry, hematology, coagulation tests, thyroid function) should be performed within 14 calendar days prior to the first study dose.

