Appropriate resuscitation equipment should be available at the bedside and a physician readily available during the period of drug administration. For further information, please refer to the Common Terminology Criteria for Adverse Events v5.0 (CTCAE) at <http://ctep.cancer.gov>

Table 7.3:3 Dose Modification and Toxicity Management Guidelines for Immune-related Adverse Events Associated with Pembrolizumab

Immune-related Adverse Event	Toxicity Grade or Conditions (CTCAE v5.0)	Action Taken with Pembrolizumab	irAE Management with Corticosteroids and Other Therapies	Monitoring and Follow-up
General instructions:				
	Grade 2	Withhold	Administer corticosteroids (initial dose of 1 to 2 mg/kg prednisone or equivalent) followed by taper Add prophylactic antibiotics for opportunistic infections	Monitor participants for signs and symptoms of pneumonitis Evaluate participants with suspected pneumonitis with radiographic imaging and initiate corticosteroid treatment
	Recurrent Grade 2, Grade 3 or 4	Permanently discontinue		
	Grade 2 or 3	Withhold	Administer corticosteroids (initial dose of 1 to 2 mg/kg prednisone or equivalent) followed by taper	Monitor participants for signs and symptoms of enterocolitis (ie, diarrhea, abdominal pain, blood or mucus in stool with or without fever) and of bowel perforation (ie, peritoneal signs and ileus)
	Recurrent Grade 3 or Grade 4	Permanently discontinue		Participants with \geq Grade 2 diarrhea suspecting colitis should consider GI

Immune-related Adverse Event	Toxicity Grade or Conditions (CTCAE v5.0)	Action Taken with Pembrolizumab	irAE Management with Corticosteroids and Other Therapies	Monitoring and Follow-up
				consultation and performing endoscopy to rule out colitis Participants with diarrhea/colitis should be advised to drink liberal quantities of clear fluids. If sufficient oral fluid intake is not feasible, fluid and electrolytes should be substituted via IV infusion
AST / ALT elevation or Increased bilirubin	Grade 2 ^a	Withhold	Administer corticosteroids (initial dose of 0.5 to 1 mg/kg prednisone or equivalent) followed by taper	Monitor with liver function tests (consider weekly or more frequently until liver enzyme value returned to baseline or is stable)
	Grade 3 ^b or 4 ^c	Permanently discontinue	Administer corticosteroids (initial dose of 1 to 2 mg/kg prednisone or equivalent) followed by taper	

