8.4.1. Initial Follow-up

Unless subjects withdraw consent or are lost to follow-up, subjects who discontinue study treatment will be followed for acquisition of safety information for 30 days (+7 days) after the final dose of study treatment. All AEs that occur prior to the Initial Follow-up Visit should be recorded. AE of Grade >1 will be followed until the resolution of the AE to Grade 0-1 or until the beginning of a new anticancer therapy, whichever occurs first.

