8.5. Unscheduled Visit

In addition to regular study visits, an unscheduled visit can be placed during the study as required, for example, if adverse event, such as cardiac dysfunction or elevation of hepatic enzymes is suspected, or further tests are needed for follow-up of the AEs. For this, the investigator will inform subjects of this during regular study visits and instruct them to have a contact the investigator immediately if they have experienced AEs. The corresponding visits must be recorded in both eCRF and source documents.

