11.4.3. Safety Analysis

All adverse events will be coded using the most recent version of the Medical Dictionary for Regulatory Activities (MedDRA) coding dictionary, graded using NCI-CTCAE version 5.0 and listed by subject.

Statistical analysis and reporting of adverse events will concentrate on treatment-emergent adverse events (TEAEs). To this end, all adverse events occurring from the first dose of the study treatment through 30 days following cessation of study treatment will be considered 'treatment-emergent'. Adverse events that start before first study treatment and deteriorate under treatment will also be considered as 'treatment-emergent'.

Incidence of TEAEs will be summarized by maximum severity and causal relationship with either FLX475 or pembrolizumab using System Organ Class(SOC) and Preferred Term(PT) of MedDRA. Incidence of ECIs, SAEs, TEAEs leading to dose modification (reduction/interruption), drug discontinuation or death also be summarized respectively, and the list will be provided as appropriately.

Adverse events reported prior to treatment but after informed consent will be provided in a listing.

Laboratory test result will be summarized both quantitatively as well as qualitatively by planned time point. For the quantitative parameter, the actual value and the change from baseline will be summarized using System International (SI) units. Shift table, which display a cross-tabulation of the baseline grade versus the worst grade until ED/EOT will be provided for both of the NCI-CTCAE(v5.0) grade and investigator's clinical significance abnormality assessment.

Vital signs and 12-Lead ECG parameter will be summarized descriptive statistics for the actual value and the change from baseline. In addition, for 12-Lead ECG parameter, the shift table will be presented for the investigator's clinical significance abnormality assessment.

All clinically significant abnormality from the laboratory test, vital signs, and 12-Lead ECG will be classified according to NCI-CTCAE(v5.0) and also be reported as adverse events.

[REDACTED]

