#### 13.1 Adverse Events

All AEs including will be coded using the most recent version of the MedDRA coding dictionary, graded using NCI-CTCAE version 5.0.

Treatment emergent adverse events (TEAEs) are defined as adverse events occurring from the first dose of the study treatment through 30 days following cessation of study treatment will be considered 'treatment-emergent'. Adverse events that start before first study treatment and deteriorate under treatment will also be considered as 'treatment-emergent'.

All AE summaries will be restricted to TEAEs only and all the study drug related AE will be summarized [REDACTED]. Summary tables will include the number of participants (%) experiencing an event and the number of events. Subjects will be counted only once for each SOC and PT level (categorical descriptive analysis). For each TEAE, the most extreme grade recorded in eCRF will be attributed and used in the by-severity summaries.

The TEAE summaries will include:

- Overall summary of TEAEs
- Summary of TEAEs by SOC and PT
- Summary of TEAEs by SOC, PT and Severity
- Summary of SAEs by SOC and PT
- Summary of SAEs by SOC, PT and Severity
- Summary of ECIs by SOC and PT
- Summary of ECIs by SOC, PT and Severity
- Summary of TEAEs Related to (any study drug [REDACTED]) by SOC and PT
- Summary of TEAEs Related to (any study drug [REDACTED]) by SOC, PT and Severity
- Summary of SAEs related to (any study drug [REDACTED]) by SOC and PT
- Summary of TEAEs leading to (any study drug [REDACTED]) dose modification (reduction / interruption) by SOC and PT
- Summary of TEAEs leading to (any study drug [REDACTED]) discontinuation by SOC and PT
- Summary of TEAEs leading to death by SOC and PT

Separate by-subject data listings will be created for

- TEAEs
- SAEs
- TEAEs leading to dose modification (reduction/interruption)
- TEAEs leading to drug discontinuation
- TEAEs leading to death
- Adverse events reported prior to treatment but after informed consent

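### The worst-grade laboratory shift table ends at ED/EOT while adverse events count to day 30, so laboratory grades first reached in between are missed

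*SAP*

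**What the plan says.** SAP 13.2 cross-tabulates baseline grade against the "worst grade that observed in planned and unplanned visits until ED/EOT". It does so for both the CTCAE grade and the investigator's assessment of clinical significance. Protocol 11.4.3 sets the same limit: "a cross-tabulation of the baseline grade versus the worst grade until ED/EOT".

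Protocol Table 1.2:1, footnote u, fixes the timing of ED/EOT: the assessments "must be performed within 14 days following the subject's last administration of study treatment", and before any other treatment begins.

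The adverse event window is longer. SAP 13.1 defines treatment-emergent events as "adverse events occurring from the first dose of the study treatment through 30 days following cessation of study treatment".

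The other laboratory tables in SAP 13.2 are by-visit summaries. The same section restricts summary tables to scheduled results and sends everything else to the listings. The shift table departs from that restriction without saying that it is an exception.

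**The concern.** Two safety displays in one report end at different times. A laboratory abnormality that first appears or worsens after ED/EOT can count as a treatment-emergent event at its highest grade, while the shift table shows only the lower grade seen by ED/EOT.

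The protocol plans for results in that interval:

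- For hepatic immune-related events, Table 7.3:3 instructs: "Monitor with liver function tests (consider weekly or more frequently until liver enzyme value returned to baseline or is stable".
- Section 8.4.1 provides that an "AE of Grade >1 will be followed until the resolution of the AE to Grade 0-1", or until new anticancer therapy starts.
- Section 8.5 allows unscheduled visits when hepatic enzyme elevation is suspected "or further tests are needed for follow-up of the AEs", and requires them to be recorded in the eCRF.

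Safety and tolerability is a secondary objective assessed partly on laboratory data. A worst-grade table that leaves out collected post-treatment results can understate that part of the safety profile.

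**Working it through.** The plan gives no figure to reproduce, so the check compares the two windows and then asks what can fall between them.

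**Inputs**
- End of the shift table: ED/EOT (SAP 13.2, Protocol 11.4.3).
- Planned ED/EOT: day 0 to day 14 after the last administration (Protocol Table 1.2:1, footnote u).
- End of the TEAE window: day 30 after cessation (SAP 13.1).
- Assumption: cessation and last administration are the same date.

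**Uncovered period** = TEAE end minus ED/EOT day
- ED/EOT on day 14: 30 − 14 = 16 days, and 16/30 = 53% of the post-treatment TEAE window.
- ED/EOT on day 0: 30 − 0 = 30 days, or 100%.

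**Which results fall there.** The schedule footnotes place the last planned chemistry, hematology, coagulation and thyroid samples at ED/EOT. Protocol 8.4.2 names only ECG and PK sampling for the 30-day visit. Later laboratory results are therefore unscheduled or part of adverse event follow-up.

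**Where those results are reported**
- By-visit summaries: no, because these take scheduled results only.
- Shift table: no, because it has closed.
- Listings: yes.
- TEAE tables: only if the abnormality is reported as an adverse event. Protocol 9.2.1 makes that depend on the investigator's judgement of clinical significance or on an intervention, withdrawal or withholding of treatment. Table 7.3:1, footnote f, itself foresees Grade 3 or higher amylase and lipase elevations that the investigator does not consider clinically relevant.

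**Direction.** Let W(T) be the highest post-baseline grade measured up to time T. If T2 is later than T1, then W(T2) ≥ W(T1), because a maximum over more results cannot be smaller. Closing the table early can lower a subject's worst grade or leave it unchanged. It cannot raise it.

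**Size.** The documents give no rate of laboratory toxicity, of sampling after ED/EOT, or of grade changes after ED/EOT, so the number of subjects cannot be derived. Each affected subject would move a cell by 1/60 = 1.7 percentage points in Cohort 1 at its maximum size, and by 1/30 = 3.3 points in Cohort 2 at its maximum.

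**The case against.** A reader might infer that the table leaves out the peak values of the toxicities that made subjects stop, and hence that Grade 3–4 laboratory rates are materially too low. The documents do not support that, for four reasons.

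- A toxicity that leads to stopping is normally measured before the decision, and the table keeps every result up to ED/EOT, unscheduled ones included. Only a higher grade first measured later is missed.
- Under Table 7.3:3, hepatic and renal immune-related events lead to permanent discontinuation of pembrolizumab at Grade 3 or 4. Subjects stopped under those rules have generally already entered the Grade 3–4 cells by ED/EOT. For them the likely loss is a further rise from Grade 3 to 4.
- Clinically significant abnormalities are also reported as adverse events (Protocol 11.4.3). SAP 13.1 uses the most extreme recorded grade, and events of clinical interest, which include a hepatic laboratory criterion, have their own tables. Such peaks are not lost from the report.
- The 16-day gap is a planned minimum, not a firm bound. SAP 3.1 applies no visit windows, so a late ED/EOT still counts. Assessments continue while dosing is interrupted, and if one drug continues alone, ED/EOT moves later with it.

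It is also fair to say that the SAP follows the protocol, that ED/EOT is a natural limit because it holds the last scheduled sample, that the ECOG shift table uses the same limit, and that no formal testing or stated decision rule depends on this table.

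All of this limits the size of the problem and makes it an analysis choice rather than a deviation. It does not remove the gap. Late-onset abnormalities, further rises after ED/EOT, and abnormalities not reported as adverse events remain outside the table.

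**Conclusion.** The point holds in a limited form. With an on-time ED/EOT, the shift table leaves uncovered 16 to 30 of the 30 post-treatment days that the TEAE tables cover. A grade first reached in that period is absent from the only visible laboratory table that uses unscheduled post-baseline results. The effect is one-directional, towards understating the worst grade. Its size is unknown, and nothing in the documents supports an estimate of the number of subjects.

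This rests on three assumptions: that laboratory values from unscheduled visits after ED/EOT are entered in the eCRF along with the visits; that cessation and last administration coincide; and that no other worst-grade laboratory table is planned. The last cannot be confirmed, because the SAP's list of tables is redacted.

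The change is worth making because it costs little and uses data already collected. It does not threaten the primary analysis.

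**What to change.** In SAP 13.2, take the worst grade over all planned and unplanned results through the later of ED/EOT and 30 days after cessation of study treatment. Three details matter:

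- Taking the later of the two dates keeps an ED/EOT visit done after day 30, which a plain 30-day limit would drop.
- Do not add a cut at the start of new anticancer therapy. SAP 13.1 has none, and adding one would create a new mismatch.
- State that the shift table is an exception to the sentence in 13.2 that limits summary tables to scheduled results.

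Record the departure from Protocol 11.4.3 in SAP section 15, which now reads as not applicable.

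The cost is one change to the analysis window and a footnote, with no new data collection. Results after ED/EOT will be sparse and will come mainly from subjects under follow-up for an adverse event, so the footnote should say so. Reported laboratory toxicity may look slightly less favourable. Peaks measured after both day 30 and ED/EOT will still be outside the table.

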### **13.3 Vital Signs**

The following vital signs measurements will be taken at the time points specified in the Schedule of Events (refer to the Protocol):

- Systolic blood pressure (SBP) (mmHg)
- Diastolic blood pressure (DBP) (mmHg)
- Pulse rate (bpm)
- Respiratory rate (breaths per minutes)
- Temperature (C)

All vital signs data collected at scheduled and unscheduled visits will be included in the listings, but only results collected as scheduled visits will be included in the summary tables.

The parameter names that will be used in the outputs will comprise of the test name and the unit of measure, for example, 'Systolic Blood Pressure (mmHg)'. Parameters will be sorted in the order that the measurements were collected in on the Vital Signs eCRF page within the tables and listings.

Vital signs measurements will present summary statistics for the results at the baseline and each scheduled post-baseline visit for each of the parameters. In addition, summaries will be presented for the change from baseline values at each scheduled post-baseline visit (continuous descriptive analysis).

The decimal precision to which the summaries for each parameter will presented will be based on the maximum number of decimals to which the results were reported on the eCRF.

### **13.4 12-Lead Electrocardiogram (ECG)**

The following ECG measurements will be taken at the time points specified in the Schedule of Events (refer to the Protocol):

- Heart Rate (beats/min)
- PP Interval (msec)
- RR Interval (msec)
- QRS Interval (msec)
- QT Interval (msec)
- QTcB Interval (msec)
- QTcF Interval (msec)

All ECG data collected at scheduled and unscheduled visits will be included in the listings, but only results collected as scheduled visits/time points will be included in the summary tables.

The parameter names that will be used in the outputs will comprise of the test name and the unit of measure, for example, 'Heart Rate (beats/min)'. Parameters will be sorted in the order that the measurements were transferred from the external vendor [REDACTED] within the tables and listings.

ECG measurements will present summary statistics for the results at the baseline and each scheduled post-baseline visit for each of the parameters. In addition, summaries will be presented for the change from baseline values at each scheduled post-baseline visit/time points (continuous descriptive analysis).

Summary of the number and percentage of subjects with average QTcF intervals (< 450ms, 450 – 480 ms, 481 – 500 ms, >= 501 ms) by visit/time point will be provided, as well as summary of the number and percentage of subjects with specific increases from baseline in QTcF intervals (<= 30 ms, > 30 ms, or > 60 ms) by visit/time point.

Since triplicate tracings are done as part of one assessment, the mean of the three tracings per parameter will be summarized for each subject. All values will be listed including the mean value per parameter. Changes from baseline will be calculated based on the mean values of the triplicates where appropriate.

The decimal precision for each parameter will be based on the maximum number of decimals to which the results were reported on the eCRF.

[REDACTED]

